#### Use of basal insulin

The type of basal insulin must remain the same throughout the study, if possible.

In case of hypoglycemic episode(s), please refer to Section 6.5.2.

If the participant experiences acute illness with hyperglycemia, unlimited insulin therapy may be used for up to 2 weeks. After that time, the participant's basal insulin dose should be at the baseline dose (including up to  $\pm 15\%$  of baseline dose) and other insulins (if used) should be stopped. This does not constitute rescue.

# 7. Discontinuation of Study Intervention and Participant Discontinuation/Withdrawal

Discontinuation of specific sites or of the study as a whole are handled as part of Appendix 1, Section 10.1.

# 7.1. Discontinuation of the Study Intervention

In rare instances, it may be necessary for a participant to permanently discontinue study intervention. If study intervention is permanently discontinued, the participant will remain in the study and complete all study visits and procedures as outlined in the SoA (Section 1.3).

This list describes circumstances in which participants will be discontinued from the intervention:

- If participants develop confirmed pancreatitis (if not confirmed, study intervention may be restarted) (see Section 8.3.3.3)
- If a participant is diagnosed with MTC or C-cell hyperplasia after randomization or has calcitonin value ≥35 ng/L that has increased at least 50% over baseline after randomization
- If a participant is diagnosed with an active malignancy or if a previously treated malignancy becomes known after randomization
- If a participant becomes pregnant
- If a participant is diagnosed with T1DM
- Any significant study intervention-related hypersensitivity reaction
- Any other treatment-emergent adverse events (TEAE), SAE, or clinically significant laboratory value for which the investigator believes that permanent study intervention discontinuation is the appropriate measure to be taken, or
- If a participant requests to discontinue intervention.

Participants who stop the study intervention permanently will receive another glucose-lowering medication, if needed per clinical judgment of investigator, and will continue participating in the study according to the protocol to collect all planned efficacy and safety measurements per Section 1.3 (SoA), Section 8.3 (Adverse Events), and Section 8.2 (Safety Assessments) of this protocol. The new glucose-lowering medication will be recorded on the eCRF for antihyperglycemic medications.

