# 8.3.3.4. Thyroid C-Cell Hyperplasia and C-Cell Neoplasms

Individuals with personal or family history of MTC and/or MEN2 will be excluded from the study.

The assessment of thyroid safety during the study will include reporting of any case of thyroid malignancy including MTC and papillary carcinoma and measurements of calcitonin. Calcitonin measurements will assess the potential of tirzepatide to affect thyroid C-cell function, which may indicate development of C-cell hyperplasia and neoplasms. These data will be captured in specific eCRFs.

If an increased calcitonin value ( $\geq$ 35 ng/L AND an increase by  $\geq$ 50% compared with baseline) is observed in a participant who has administered a medication that is known to increase serum calcitonin, this medication must be stopped and calcitonin levels must be measured after an appropriate washout period. A consultation with a thyroid specialist or an endocrinologist, should be obtained. See Section 7.1 for thyroid-related discontinuation criteria.

If the confirmed calcitonin value is <35 ng/L, tirzepatide should be restarted when it is safe to do so.

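### Protocol Sections 7.1 and 8.3.3.4 share one calcitonin trigger but conflict when the repeat value is below 35 ng/L

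*Protocol*

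**What the plan says.** Protocol Section 7.1 opens with permanent cessation: "In rare instances, it may be necessary for a participant to permanently discontinue study intervention". Its list is mandatory in tone: "This list describes circumstances in which participants will be discontinued from the intervention". One entry is a participant who "has calcitonin value ≥35 ng/L that has increased at least 50% over baseline after randomization". That entry has no retest, no exception and no pointer to another section. The pancreatitis entry in the same list does carry a qualifier, "if not confirmed, study intervention may be restarted", and a cross-reference.

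Protocol Section 8.3.3.4 sets the same threshold ("35 ng/L AND an increase by" 50% or more). It says that when such a value "is observed in a participant who has administered a medication that is known to increase serum calcitonin, this medication must be stopped", calcitonin is to be measured again after a washout and a specialist consulted. It refers to Section 7.1 for the thyroid-related discontinuation criteria. A separate paragraph then says: "If the confirmed calcitonin value is <35 ng/L, tirzepatide should be restarted when it is safe to do so".

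In the SAP, Table GPGV.3.1 removes data collected after discontinuation of study intervention from EAS1 and EAS2. FAS and FAS2 keep data regardless of adherence.

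**The concern.** A restart instruction presupposes that tirzepatide was stopped for a time and that a confirmatory value was obtained. Section 7.1 provides for neither. A site working from Section 7.1 would stop study intervention for good. A site working from Section 8.3.3.4 could resume it in the same participant once the repeat value came back below 35 ng/L. Neither section says which prevails.

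This is a stopping rule for an adverse event of special interest in participants aged 10 to under 18, so consistent handling matters in its own right. It also reaches the reporting. Intervention discontinuation is an intercurrent event of the efficacy estimand, and discontinuation due to adverse events is a listed safety endpoint.

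**Working it through.** The plan gives no figure to reproduce. The check compares the two passages, with a little arithmetic on the trigger.

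**Trigger.** Both sections require a value of at least 35 ng/L and at least 50% above baseline. The joint trigger is therefore max(35, 1.5 × baseline). Exclusion criterion 31 requires a Visit 1 value below 35 ng/L.

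- The two limits cross at 35 / 1.5 = 23.3 ng/L. Up to that baseline the trigger is 35 ng/L.
- Above it the trigger is 1.5 × baseline, rising towards 1.5 × 35 = 52.5 ng/L.

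**What follows a triggering value**

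| Repeat value | Section 7.1 | Section 8.3.3.4 | Result |
|---|---|---|---|
| Below 35 ng/L | Permanent stop | Restart when safe | Conflict |
| At least 35 ng/L and at least 50% above baseline | Permanent stop | No restart | Agreement |
| At least 35 ng/L but less than 50% above baseline | Repeat value does not itself meet the criterion | Restart condition not met | No instruction |

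The third row can occur only if baseline exceeds 23.3 ng/L. Example: baseline 30 gives a trigger of 1.5 × 30 = 45; a repeat value of 40 is 40 / 30 − 1 = 33% above baseline.

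**Who is covered.** The washout and retest are written only for a participant who took a calcitonin-raising medication. The restart sentence stands alone and carries no such limit. It is also unclear whether the medication to be stopped can include study intervention. If it cannot, Section 8.3.3.4 contains no instruction to stop tirzepatide, and the only stop available to be reversed is the permanent one in Section 7.1.

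**When it can arise.** The Schedule of Activities has post-baseline calcitonin at Weeks 16, 30, 42 and 52, at early termination and at Visit 801. Tirzepatide ends at Week 52 in any case, Visit 801 is after treatment, and early termination ends participation. That leaves Weeks 16, 30 and 42.

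**Effect on the Week 30 endpoint.** Double-blind HbA1c is drawn after baseline at Weeks 4, 8, 12, 16 and 30.

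- After a Week 16 trigger handled as a permanent stop, the values at Weeks 4, 8, 12 and 16 stay in EAS1. Only the Week 30 value leaves it.
- FAS keeps the Week 30 value if it is collected. Section 7.1 has such participants remain in the study and complete all visits.
- A trigger at Week 30 or Week 42 comes too late to affect the Week 30 value. It can affect only later data, in EAS2.

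**The case against.** The best defence is that the sections describe one process: Section 8.3.3.4 is the work-up and Section 7.1 the end criterion. Section 8.3.3.4 speaks of a confirmed value and refers to Section 7.1 for the criteria. Section 7.1 does not say that one unconfirmed value is enough. Section 7.1.2 provides generally for temporary interruption and restart. This reading is coherent, but the protocol does not state it. Section 7.1 neither mentions confirmation for calcitonin nor refers to Section 8.3.3.4, and Section 7.1.2 does not mention calcitonin. The defence shows what may have been meant; it does not remove the conflict in the text.

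Two limits on the point do stand. The retest step is written for co-medicated participants only, and a repeat value that still meets the trigger produces no conflict. A reader might infer that every triggering result leads to opposite instructions. The documents do not support that.

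A reader might also infer a loss of 1 in about 30 participants per arm (1 / 30 = 3.3%). That figure is one person divided by arm size, not an effect. The primary comparison pools about 60 tirzepatide participants (1 / 60 = 1.7%), the documents give no incidence of the trigger, and EAS1 excludes later data rather than the participant.

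**Conclusion.** The text is wrong as written, within limits. For a participant who took a calcitonin-raising medication and whose repeat value is below 35 ng/L, Section 7.1 directs a permanent stop and Section 8.3.3.4 a restart. Three matters are left open: whether the medication to be stopped includes study intervention, whether the restart sentence covers participants without such a co-medication, and what follows a repeat value of at least 35 ng/L that is less than 50% above baseline.

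The main consequence is inconsistent safety handling between sites. The numerical effect is expected to be small: each Week 16 case handled as a permanent stop costs EAS1 one Week 30 HbA1c value, and FAS still includes the participant's data. The expectation of few cases is an assumption. It rests on the exclusion of Visit 1 values of 35 ng/L or more, since no incidence is given.

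It would also go too far to say that a participant who restarts certainly stays in EAS1. The SAP does not say how a stop followed by a restart is classified.

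**What to change.** Sections 7.1 and 8.3.3.4 must be reconciled so that one sequence appears in both: the trigger, whether confirmation is needed, and what follows each possible repeat result, including one of at least 35 ng/L that is less than 50% above baseline. Add cross-references each way. State which participants the sequence covers and whether the medication to be stopped can include study intervention. The sponsor's medical team decides which rule stands; this review takes no position on it.

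The cost is a short clause in each section in a protocol amendment. Whether extra repeat tests or consultations are needed depends on the decision: extending the sequence beyond co-medicated participants would add some. If the reconciled rule allows a restart, one sentence in the SAP should say how data after a stop and restart are treated in EAS1 and EAS2.

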# 7.1.1. Liver Chemistry Stopping Criteria

# Discontinuation due to a hepatic event or liver test abnormality

Participants who are discontinued from intervention due to a hepatic event or liver test abnormality should have additional hepatic safety data collected via eCRF.

The study intervention should be interrupted or discontinued if one or more of these conditions occur.

Participants with Normal or Near Normal	Participants with Elevated Baseline ALT and		
Baseline ALT and AST (<1.5x ULN) at Visit 1	AST (≥1.5x ULN) at Visit 1		
ALT or AST >5x ULN	ALT or AST >3x baseline at Visit 1		
ALT or AST >3x ULN and either TBL >2x ULN or	ALT or AST >2x baseline at Visit 1 and either TBL		
INR >1.5	>2x ULN or INR >1.5		
(Except for participants with Gilbert's syndrome) a	(Except for participants with Gilbert's syndrome) a		
ALT or AST $>3x$ ULN with the appearance of	ALT or AST >2x baseline at Visit 1 with the		
fatigue, nausea, vomiting, right upper quadrant pain	appearance of fatigue, nausea, vomiting, right upper		
or tenderness, fever, rash, and/or eosinophilia (>5%)	quadrant pain or tenderness, fever, rash, and/or		
	eosinophilia (>5%)		
All participants			
ALP >3x ULN (when the source of increased ALP is the liver)			
ALP >2.5x ULN and TBL > 2x ULN			
(Except for participants with Gilbert's syndrome) a			
ALP >2.5x ULN with the appearance of fatigue, nausea, vomiting, right upper quadrant pain or tenderness,			
fever, rash, and/or eosinophilia (>5%)			
Source: FDA Guidance for Industry: Drug-Induced Liver Injury: Premarketing Clinical Evaluation, July 2009			
and other consensus guidelines, with minor modifications			
Abbreviations: ALP = alkaline phosphatase; ALT = alanine aminotransferase; AST = aspartate aminotransferase; TBL = total bilirubin; ULN = upper limit of normal.			
a In participants with Gilbert's syndrome, doubling of direct bilirubin should be used for drug interruption or discontinuation decisions rather than TBL>2x ULN.			

Resumption of the study intervention can be considered only in consultation with the Lilly-designated medical monitor and only if the liver test results return to baseline and if a self-limited non-drug etiology is identified.

See Section 8.2.8 (Hepatic Monitoring) and Appendix 6, Section 10.6 (Liver Safety: Suggested Action and Follow-Up Assessments) for further guidance on Hepatic monitoring.

#### 7.1.2. Temporary Discontinuation

In certain situations, the investigator may need to temporarily interrupt study intervention. Every effort should be made by the investigator to maintain participants on study intervention and to restart after any temporary interruption, as soon as it is safe to do so.

The data related to temporary interruption of study intervention will be documented in source documents.

This table shows how to manage treatment if there are missed study treatment doses.

If the number of missed study treatment doses is	Then
2 or less	the study treatment can be restarted at the last administered dose, if it was well tolerated prior to interruption.
3 or more	the IWRS will dispense 5 mg tirzepatide irrespective of the dose the participant was receiving before the interruption and subsequently escalate as required by the protocol.

Abbreviations: IWRS = interactive web-response system.

If the study treatment interruption is due to intolerable persistent GI AE, such as nausea, vomiting, or diarrhea, the participant should be treated as suggested in Section 6.5.4.

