# **Intervention Groups and Duration:**

The overall study duration is approximately 60 weeks over 4 required study periods. This table describes the study periods.

[figure not shown]
Study Period	Duration	Intervention
Screening/lead-in	Approximately 4 weeks	
Double-blind, placebo-controlled	30 weeks	5 mg tirzepatide 10 mg tirzepatide, or placebo
Open-label extension on active treatment period	22 weeks	5 mg tirzepatide, or 10 mg tirzepatide
Post-treatment safety follow-up	30 days	

In the 22-week open-label period, participants in 5 mg and 10 mg arms will continue with current treatment while participants randomized to placebo will initiate treatment at 2.5 mg QW and after 4 weeks, will receive 5 mg tirzepatide for the remainder of the period.

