# 4.2. Scientific Rationale for Study Design

This is a superiority study, the main objective of which is to compare the effects of tirzepatide 5 mg and tirzepatide 10 mg QW (pooled), with metformin or basal insulin, or both to those on placebo for glycemic control (defined as change from baseline in HbA1c) in pediatric and adolescent population with T2DM over a 30-week period, followed by a 22-week open-label extension.

The efficacy measure, HbA1c, was chosen as the primary objective because it is an accepted endpoint in glycemic studies in pediatric and adolescent participants with T2DM.

The use of placebo for 30 weeks during the double-blind portion of the study is considered appropriate, as Phase 3 studies with tirzepatide have not been conducted to date in the pediatric and adolescent population. Thus, a placebo comparator is necessary to understand tirzepatide's true safety and efficacy. To protect the safety of the participants enrolled across all arms of this study, the double-blind period is relatively short, there are clear rescue criteria for participants with severe, persistent hyperglycemia (see Section 8.3.3.2) and participants are allowed to decrease basal insulin and/ or metformin as needed if hypoglycemia occurs (for the definition of hypoglycemia, see Section 8.3.3.1).

The doses of tirzepatide for this study were based on efficacy, safety and PK/PD data from two placebo-controlled studies in adults with T2DM, SURPASS-1 (GPGK), monotherapy study versus placebo and SURPASS-5 (GPGI), add-on to basal insulin vs placebo.

To mitigate the occurrence of GI AEs and permit time for the development of tolerance to GI effects, a dose escalation scheme will be used that starts at a low dose of 2.5 mg QW for 4 weeks and then escalates 2.5 mg increments every 4 weeks (Section 6.5.1). Therefore, it will take 4 weeks of dosing to reach a maintenance dose of 5 mg and 12 weeks to reach a maintenance dose of 10 mg.

The background therapies of diet and exercise, with metformin or basal insulin or both, are considered appropriate, as these are approved treatments for pediatric and adolescent participants with T2DM in the US, EU, and many countries around the world.

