# 6.1. Study Intervention(s) Administered

Study intervention will be self-administered by the participant or administered to the participant by the parent/caregiver.

This table describes the interventions administered in this study.

Intervention Name	Tirzepatide (LY3298176)	Placebo
Туре	Intervention	Intervention
Dose Formulation	Single dose pen (SDP)	SDP
Unit Dose Strength(s)	2.5 mg, 5 mg, 7.5 mg, 10 mg	Not applicable
Dosage Level(s)	5 mg, 10 mg	Not applicable
Dose Volume	0.5 mL	0.5 mL
Route of Administration	SC injection	SC injection
Use	Experimental	Placebo
IMP and NIMP	IMP IMP	
Sourcing	Provided centrally by the Sponsor and dispensed by IWRS	
Packaging and Labeling	Study intervention will be provided in single dose pens and packaged in cartons to be dispensed.	
	Clinical study materials will be labeled according to country regulatory requirements.	

Abbreviations: IMP = investigational medicinal product; IWRS = interactive web-response system; NIMP = non-investigational medicinal product; SC = subcutaneous; SDP = single dose pen.

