# 6.5. Dose Modification

# **6.5.1.** Tirzepatide Dose Escalation

The dose escalation scheme consists of a starting dose of 2.5 mg QW accompanied by a dose escalation of 2.5 mg increments every 4 weeks until the desired dose level is reached and maintained for the duration of the study.

This figure illustrates the tirzepatide dose escalation regimen.

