# 6.5.4. Management of Gastrointestinal Symptoms

During the double-blind dose escalation period, every effort must be made by the investigator to maintain participants on the dose assigned by IWRS.

This table describes steps the investigator should follow to mitigate GI symptoms and manage participants with intolerable GI AEs during the escalation period.

STEP 1	Advise participants to eat smaller meals, for example, splitting 3 daily meals into 4 or more smaller meals, and to stop eating when they feel full.
STEP 2	Continue STEP 1 +  Prescribe symptomatic medication, for example, anti-emetic or anti-diarrheal medication, per local country availability and individual participant needs. Use of symptomatic medication should be captured as concomitant medication in the eCRF.
STEP 3	Continue STEP 1 + STEP 2 +  Temporarily interrupt tirzepatide; omit 1 dose, the participant will take 3 of 4 doses at that dose level. After the interruption, the investigator should restart the dose or escalate the dose as required, with the participant taking medication to alleviate their GI symptoms. The data related to temporary interruption of study treatment should be documented in source documents.
STEP 4	If intolerable GI symptoms or events persist despite the above measures, the investigator may decide to discontinue study intervention permanently.  Participants who stop study intervention permanently will intensify insulin treatment and/or receive another glucose-lowering intervention (Section 7.1) and will continue participating in the study according to the protocol to collect all planned efficacy and safety measurements. The new glucose-lowering intervention will be recorded on the eCRF for collecting anti-hyperglycemic medications.

Note: De-escalation of study intervention will not be allowed.

Abbreviations: eCRF = electronic case report form; GI = gastrointestinal.

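### After three or more missed doses, Protocol 7.1.2 makes a participant whose last dose was 2.5 mg step up to 5 mg, possibly after a single 2.5 mg injection

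*Protocol*

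**What the plan says.** Protocol Section 7.1.2 sets the restart dose by the number of missed doses.

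- Two or fewer: "the study treatment can be restarted at the last administered dose, if it was well tolerated prior to interruption".
- Three or more: "the IWRS will dispense 5 mg tirzepatide irrespective of the dose the participant was receiving before the interruption", then escalation as the protocol requires.

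The 2.5 mg step applies to everyone who receives tirzepatide. Section 4.2 describes a scheme that "starts at a low dose of 2.5 mg QW for 4 weeks and then escalates 2.5 mg increments every 4 weeks", and gives its purpose as limiting GI adverse events while tolerance develops. Section 6.5.1 repeats it: "a starting dose of 2.5 mg QW accompanied by a dose escalation of 2.5 mg increments every 4 weeks". In the open-label period, according to the Synopsis, "participants randomized to placebo will initiate treatment at 2.5 mg QW and after 4 weeks, will receive 5 mg tirzepatide". Section 6.1 lists the pen strengths as "2.5 mg, 5 mg, 7.5 mg, 10 mg".

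Other sections also let a participant receive fewer than four doses at a step. Section 6.5.4 Step 3, for intolerable GI events, says "omit 1 dose, the participant will take 3 of 4 doses at that dose level". Section 6.1.1 requires a late dose to be skipped when the next one is less than 72 hours away. Section 6.5.3 rules out changing the tirzepatide dose.

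Neither document exempts the 2.5 mg step from the second row of 7.1.2. The SAP (Section 4.6.1) mentions only an optional listing of participants with three or more consecutive missed doses.

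**The concern.** The row for three or more missed doses looks like a re-titration rule, and from 7.5 or 10 mg it works as one. At 2.5 mg it works the other way: a child who has had little drug and a long break is given twice the last dose. The row is mandatory, and Section 6.5.3 leaves the investigator no evident route to 2.5 mg.

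What is at stake is GI tolerability at the first step, in either tirzepatide arm from Week 0 and in former placebo participants from Week 30. Because Section 7.1.2 refers interruptions for persistent intolerable GI events to Section 6.5.4, the row mainly governs interruptions for other reasons.

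**Working it through.** **The plan's own schedule.** Weeks to reach dose D = 4 × (D − 2.5)/2.5. For 5 mg this is 4 × 1 = 4 weeks; for 10 mg it is 4 × 3 = 12 weeks. Both match Section 4.2.

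**Restart dose by last dose.** The second column assumes that the permissive option in the first row of 7.1.2 is used.

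| Last dose | 2 missed | 3 missed | Change from last dose with 3 missed |
|---|---|---|---|
| 2.5 mg | 2.5 mg | 5 mg | +2.5 mg (doubled) |
| 5 mg | 5 mg | 5 mg | none |
| 7.5 mg | 7.5 mg | 5 mg | −2.5 mg |
| 10 mg | 10 mg | 5 mg | −5 mg |

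Only the 2.5 mg line goes up.

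**Exposure before 5 mg.** With k weekly doses taken (Weeks 0 to k − 1) and m consecutive doses missed, the restart week is k + m and the gap is 7(m + 1) days. For k = 1 and m = 3, restart is at Week 4 after 28 days. The number of 2.5 mg injections before 5 mg is:

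- 4 as planned;
- 3 under Section 6.5.4 Step 3;
- 2 under the two-or-fewer row, if missed doses do not lengthen the step;
- as few as 1 under the three-or-more row.

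The nearest comparison is therefore 1 against 2, not 1 against 4.

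Using the half-life of about 5 days (Protocol Introduction) and simple exponential decline, the fraction left is 0.5^(21/5) = 5.4% after two missed doses and 0.5^(28/5) = 2.1% after three.

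**Effect of restarting at 2.5 mg, 10 mg arm, exactly three doses missed.** 10 mg follows the restart by 8 weeks under the current row and by 12 weeks under the change.

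| 2.5 mg doses taken | Restart week | 10 mg reached: now | 10 mg reached: changed | Weeks on 10 mg before Week 30: now / changed |
|---|---|---|---|---|
| 1 | 4 | 12 | 16 | 18 / 14 |
| 2 | 5 | 13 | 17 | 17 / 13 |
| 3 | 6 | 14 | 18 | 16 / 12 |
| 4 | 7 | 15 | 19 | 15 / 11 |

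**Open label.** A former placebo participant is dosed at Week 30, misses Weeks 31 to 33 and restarts at Week 34. The 5 mg dose is reached at Week 34 now (52 − 34 = 18 weeks left) or at Week 38 under the change (52 − 38 = 14 weeks left).

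**Supply.** The Schedule of Activities distributes study drug at Weeks 0, 4, 8, 12, 16, 30, 34 and 42. A 10 mg step at Weeks 17 to 19 falls after the last distribution before Week 30. An open-label 5 mg step at Week 38 falls on a telephone visit. Without extra supply it would wait until Week 42, leaving 52 − 42 = 10 weeks.

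**The case against.** The strongest reply is that a single restart dose is simple and puts nobody ahead of schedule. A participant who misses three doses on the 2.5 mg step cannot restart before Week 4, when 5 mg is the calendar dose. This is correct. The answer is only that time off drug does not give the exposure on which Section 4.2 relies for tolerance.

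Second, a reader might infer that the longer gap always leads to a higher dose than the shorter one. The documents do not establish that. The two-or-fewer row is optional and depends on tolerability, and nothing says whether missed doses lengthen a step. Take a child dosed at Weeks 0 and 1 who misses Weeks 2 and 3. That child might restart at 2.5 mg at Week 4, or might move to the scheduled 5 mg. On the second reading, the contrast with a child who missed three doses disappears. What remains is that one row permits 2.5 mg and the other excludes it.

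Third, a reader might treat Section 6.5.4 Step 3 as the only tolerance for an incomplete step. It is not: the adjacent row of 7.1.2 and the skip rule in Section 6.1.1 also allow one.

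Fourth, restarting at 2.5 mg complicates supply. That is a real cost. It is not new in kind: the current row already gives restarts at Weeks 5 to 7 and 10 mg steps at Weeks 13 to 15, which lie between distribution visits.

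**Conclusion.** The point holds on the literal text and is minor. The 2.5 mg step is the only one at which the mandatory row raises the dose after a long interruption. In the extreme case it doubles the dose after one injection and at least 28 days without drug. It is weaker for a participant who completed all four 2.5 mg doses before the gap.

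This assumes that the missed doses are consecutive within one interruption, that the row's wording covers 2.5 mg as it does every other dose, and that the IWRS follows the protocol text; its configuration is not in these documents. No frequency is given, and the case is probably rare.

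Two stronger readings are unsupported. The row does not accelerate the escalation calendar, and nothing in the documents indicates that it affects the treatment estimates, power or type I error.

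**What to change.** Reword the second row of the table in Protocol 7.1.2 to: *5 mg, or 2.5 mg if the last administered dose was 2.5 mg (tirzepatide or matching placebo per assigned arm), then escalate every 4 weeks to the assigned dose.* Align the IWRS with the new text. The 2.5 mg pen is already supplied.

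The cost is about four weeks' delay in reaching the maintenance dose for the few participants affected. With exactly three doses missed, the 10 mg arm still has 11 to 14 weeks on 10 mg before Week 30. Some off-schedule or mixed-strength dispensing is also needed where the later step falls between distribution visits. The supply arrangement should be settled with the rewording, so that an open-label step due at Week 38 does not slip to Week 42. Design, sample size and alpha are unchanged.
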